#### **6.4. WITHDRAWAL CRITERIA AND EXPECTED ANALYSIS OF WITHDRAWALS AND DROPOUTS**

Patients will discontinue the clinical trial if at least one of the following occurs:

- When the patient is uncooperative or fails to comply with the requirements of the study.
- When the investigator considers that the patient's health is compromised.
- Serious adverse event(s) that in the investigator's judgment necessitates withdrawal. (Toxicity grade IV on the WHO scale of adverse effects).
- Serious protocol violation.
- Withdrawal of consent by the patient.
- Loss of follow-up.

Patients will be informed that they can leave the clinical trial at any time they wish without any detriment to their subsequent medical care. The investigator may also, at his discretion, suspend treatment in patients in whom any of the following reasons appear:

- Refusal to receive treatment.

- Concomitant illness.
- Major protocol violations.
- Requirement of the patient.
- Non-compliance with the established visits.
- Administrative reasons.
- Loss of patient follow-up.
- Specific or general changes in the patient.

Patients who drop out of the trial for any reason are not eligible for re-inclusion.

At the time of leaving the trial, the primary cause for withdrawal from the trial should be collected and, if possible, the patient should be re-evaluated with the required tests at the End-of-Treatment visit. In the event that the cause is due to the patient's own decision, the patient will not be required to provide any explanation for this.

It should be noted that once the patient has received the administration of the investigational product (a single dose is administered), withdrawal from the study will not provide any safety benefit, so continuation of the study will be recommended.

When the investigator no longer hears from a patient, every attempt should be made to contact him/her (unless the patient has clearly expressed a wish not to be contacted) to obtain the date on which the patient was discontinued from follow-up, to establish the reason for discontinuation, to ask the patient to resume study procedures or to attend at least one last visit, and to suggest that the patient provide the contact details of the physician who will be following his/her case. If all attempts to contact the patient fail, all actions taken will be requested to be documented in the medical record, and if key study data cannot be obtained before the final visit, the investigator will then declare the patient as "lost to follow-up".

In the event of premature discontinuation of the study, the investigator should note in the CRD the reason(s) for discontinuation. If more than one reason is given, the investigator should give the primary reason.

According to good clinical practice, all patients who prematurely drop out of the study will have to be recommended for alternative treatment. If withdrawal is due to a significant adverse event, patients will be monitored by the investigator until appropriate termination, i.e., until the adverse event disappears or is determined to be permanent.

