### 6.3. EXCLUSION CRITERIA

Patients who present any of the following exclusion criteria cannot be included in the clinical trial:

- Those who in the judgment of the investigator are not in an adequate situation to tolerate the procedure.
- Clinical and anesthetic criteria that contraindicate surgery (e.g. ASA IV-V).
- Severe uncontrolled disease
- Pregnant women
- Individuals who are taking a clinical research drug or have participated in a clinical research study (with an authorized or unauthorized product) in the 30 days prior to randomization.
- Lack of informed consent or revocation of consent.
- Postoperative mechanical ventilation or thoracic surgical reintervention in the month of follow-up.

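### Sections 6.4 and 6.3 remove randomised, operated patients on avoidable grounds, and nothing requires their day-5 leak status, which conflicts with the stated intention-to-treat analysis

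*Combined protocol and SAP*

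**What the plan says.** Section 6.4 states a mandatory rule: "Patients will discontinue the clinical trial if at least one of the following occurs". Six triggers follow. Withdrawal of consent and loss to follow-up are unavoidable. Two rest expressly on the investigator's judgment: compromised health, and "Serious adverse event(s) that in the investigator's judgment necessitates withdrawal. (Toxicity grade IV on the WHO scale of adverse effects". Non-cooperation and serious protocol violation are not defined in 6.4.

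For patients who have received the single dose, the same section says that "withdrawal from the study will not provide any safety benefit, so continuation of the study will be recommended".

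Section 6.3 includes among the exclusion criteria "Postoperative mechanical ventilation or thoracic surgical reintervention in the month of follow-up". Under section 8.2, randomisation follows the screening visit and precedes product administration, so this item can only be met after randomisation and surgery.

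The primary outcome is air leak through the drains on postoperative day 5 (section 4, main objective). Sections 12 and 12.1 call for efficacy analysis by intention to treat. Section 12.2 imputes nothing for unavailable data. Its one exception, last observation carried forward, is for patient-reported records, and leak is not one of these.

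**The concern.** After surgery no trial treatment is left to stop. Ending participation then can only cost outcome data, and 6.4 itself concedes that the patient gains no safety. An intention-to-treat analysis needs the outcome in every randomised patient as far as it can be had. The exit rule works against this on grounds that are partly undefined and partly a matter of judgment, in a trial where the investigator knows the allocation.

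The 6.3 item raises a related problem. It makes a postoperative event, possibly related to air leak, a reason not to belong to the trial. Removing patients on that basis is a post-randomisation exclusion, even when their day-5 status is known.

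At stake is mainly the comparability of the arms on the primary outcome, and secondarily a little power, since the sample size carries no allowance for loss.

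**Working it through.** **1. Does any provision secure day-5 leak status after exit?**

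- 6.4, on leaving: "if possible, the patient should be re-evaluated with the required tests at the End-of-Treatment visit". This is conditional, refers to a visit that the schedule in 8.2 does not define, and does not name leak.
- 6.4, adverse events: "If withdrawal is due to a significant adverse event, patients will be monitored by the investigator until appropriate termination". This follows the event, not the leak.
- 6.4, contact attempts: these apply to patients no longer heard from, and day 5 is not named.
- 8.2, end of follow-up: a visit at 1 to 3 months, if possible, for those who discontinued. This is too late for day 5.
- 5.3, follow-up: daily assessment, including leak, while the patient is admitted. It does not say whether this continues after trial exit.
- 12.1: events in patients withdrawn early are included. This governs analysis and creates no duty to collect.

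None requires day-5 leak status.

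**2. The plan's own sample size.** Section 5.2.2 gives 27% against 13.5%, two-sided alpha 0.05 and 1:1 allocation. Its beta of 0.80 is read as power. With pooled variance and mean risk 0.2025:

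n = [1.960·√(2·0.2025·0.7975) + 0.842·√(0.27·0.73 + 0.135·0.865)]² / 0.135² = 137.9, so 138 per arm and 276 in total.

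The plan's figure reproduces and is the formula minimum. Approximate power is 80.0%. The exact figure for the uncorrected chi-square test on two binomials is 80.4%, and the exact calculation is used below.

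**3. Assumed losses.** The documents give no withdrawal rate, so every loss below is an assumption.

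*(a) Random loss, equal in both arms, at 13.5% against 27%.*

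| Lost per arm | Left per arm | Power |
|---|---|---|
| 0 | 138 | 80.4% |
| 4 (2.9%) | 134 | 79.6% |
| 7 (5.1%) | 131 | 78.5% |
| 10 (7.2%) | 128 | 77.4% |

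*(b) Only leakers lost, same share in both arms, no true effect (27% each).* Expected leakers per arm are 138 × 0.27 = 37.26. Each is lost with probability q. For a mean of 2, 4 or 7 lost per arm, the false-positive rate stays at 2.5% per side.

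*(c) Only leakers lost, experimental arm only, no true effect.* With q = mean lost / 37.26, the observed experimental risk is 0.27(1 − q)/(1 − 0.27q).

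| Mean lost | q | Observed risk | Favouring patch | Favouring control | Two-sided total |
|---|---|---|---|---|---|
| 0 | 0 | 27.0% | 2.5% | 2.5% | 5.0% |
| 1 | 2.7% | 26.5% | 3.2% | 2.0% | 5.1% |
| 2 | 5.4% | 25.9% | 3.9% | 1.5% | 5.5% |
| 4 | 10.7% | 24.8% | 6.1% | 0.9% | 7.0% |

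*(d) Only leakers lost, control arm only, planned effect, same q.* Power is 77.7%, 74.5% and 67.0%. The risk ratio is 0.51, 0.52 and 0.54 instead of 0.50.

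*(e) Four control patients lost at random, planned effect.* Power is 80.2%.

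Size of loss matters little here. Loss that depends on both leak and arm is what moves the result.

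**The case against.** The strongest reply is that the opportunity to record leak status is not missing, only the duty. Patients are normally in hospital from surgery to day 5, and leak is assessed daily with no stated exception for those withdrawn. A patient withdrawn for non-cooperation or an adverse event will often still be on the ward with a drain. Section 12.1 includes events in patients withdrawn early and leaves the data sets to be defined in a statistical analysis plan. Section 6.4 recommends continuing. Scenario (c) is also extreme: it loses leakers only, in one arm only, and never a non-leaker.

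Most of this stands, and it is why the practical risk is rated modest. Three things remain. A recommendation does not override a mandatory exit rule, and it is worded for patients who received the product, so it does not clearly cover controls. A later analysis plan cannot supply an outcome that was not collected. And the 6.3 item conflicts with intention to treat whether or not data exist.

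Three stronger readings are tempting and are not supported:

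- A reader might infer that the result will be biased towards the patch. Nothing in the documents shows that loss will differ by arm, and scenario (d) runs the other way.
- A reader might infer that the 6.3 patients will have no day-5 data. They would usually remain in hospital under daily assessment. The problem is their exclusion after randomisation.
- A reader might see a further postoperative exit in the 6.4 list that lets the investigator suspend treatment. Treatment is one intra-operative application, so after surgery that list adds almost nothing.

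**Conclusion.** The point holds as a conflict between stated rules. Followed as written, 6.4 and 6.3 can take randomised, operated patients out of the trial for reasons other than consent or true loss. No provision secures their primary outcome, none is imputed, and the analysis is nevertheless called intention to treat.

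The severity is minor to moderate. Equal random loss of up to 10 per arm costs about 3 percentage points of power (80.4% to 77.4%). Equal loss of leakers in both arms leaves the error rate unchanged. Only arm-specific loss of leakers distorts the test: 7.0% two-sided instead of 5.0% at a mean of four lost from the experimental arm, or power of 67.0% at the same loss from the control arm. Such loss cannot be excluded in an open-label trial with judgment-based triggers, but it is not shown. These sizes rest on assumed losses and on the planned rates of 27% and 13.5%. The direction of any bias is unknown.

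**What to change.** - **Section 6.4.** State that, after randomisation and surgery, only withdrawal of consent to data collection or true loss to follow-up ends participation. Record non-cooperation, compromised health, serious adverse events and protocol violations as deviations or events.
- **Day-5 status.** Require leak status through day 5 for all other randomised, operated patients in both arms, taken from the daily inpatient assessment.
- **Discharge before day 5.** Daily visits stop at discharge (5.3), or at drain removal or discharge (protocol summary, item 12), and the discharge criteria in 5.3 do not name leak. Record leak and drain status at that point and state how it counts. For example, a drain removed with no leak counts as no day-5 leak.
- **Section 6.3.** Make postoperative ventilation or reintervention a recorded event, with the patient kept in the intention-to-treat analysis.

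The no-imputation rule in 12.2 can stay, since it would then matter only for consent withdrawal or true loss.

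The cost is an amendment, plus one recorded status for patients discharged before day 5. Patients with deviations stay in the analysis and may slightly dilute the effect, as intention to treat already accepts.

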## 6.5. CLINICAL TRIAL DISCONTINUATION

The clinical trial may be discontinued in the view of any serious adverse event related to the investigational product or if any of the following circumstances arise:

1. Response < 20%
2. Severe infections > 50%
3. Failure to include a minimum of 10% of patients in the first 18 months after approval and distribution.

## 6.6. EXPECTED PATIENT ENROLLMENT

A total of 276 patients are expected to be enrolled.

## 6.7. PARTICIPANT IDENTIFICATION

Patients will be identified with the acronym HEMFAP plus a sequential numerical identification code, which will be assigned to each patient in sequential order of inclusion when they give their informed consent. In the event that a patient is included in the study, i.e. signs the informed consent, and once the procedures of the screening visit have been carried out, he/she is considered ineligible to continue in the study or the patient withdraws his/her consent, the number assigned to that patient cannot be reused for another patient.

The sponsor will only be able to identify the subjects by the number assigned to them, their date of birth and their sex. The investigator should keep a record of the names of the patients and the assigned identification number.

## 7. TREATAMENT DESCRIPTION

### 7.1. INVESTIGATIONAL PRODUCT

Investigational product: Hemopatch®

Pharmaceutical form: Collagen patch derived from bovine skin, coated with NHS-PEG (pentaerythritol polyethylene glycol ether tetrasuccinimidyl glutarate).

### 7.2. INVESTIGATIONAL PRODUCT IDENTIFICATION

The identification and labeling of the product under investigation is detailed in Annex IV.

### 7.3. INVESTIGATIONAL PRODUCT STEWARDSHIP

In the experimental group, at the end of the pulmonary lobectomy, up to 6

Hemopatch® patches are applied on the suture lines of the pulmonary parenchyma, once the absence of air leakage or minimum grade 1 according to the Machiarini scale (Annex III) has been verified. The use of the investigational product will be done in the same tissue, same location and same type of patient in which it is usually administered with the indication of hemostasis. The only difference is that in the patients participating in the clinical trial the post-surgical air leak parameter will be measured to evaluate the efficacy of HEMOPATCH® in this new indication.

They will be admitted to hospital the day before surgery and will receive standardized postoperative care; this care includes extubation of the patient in the operating room at the end of the operation, postoperative analgesia by epidural catheter with local anesthesia and fentanyl supplemented with NSAIDs, and respiratory care by physiotherapists exclusively dedicated to patients undergoing cardiothoracic surgery. The type of surgical approach will not be standardized and will be at the discretion of the surgeon, who in all cases will be an investigator of this project. The suture of the pulmonary parenchyma will be performed with mechanical staplers or resorbable hand suture material; in no case will adhesives or prosthetic material for reinforcement other than that contained in the Investigational Product be added. The pleural space will be drained with one or two 24-28 French caliber multifenestrating silicone tubes. At the end of the procedure, the drainage tube(s) will be connected to a bottle with a valvular system connected or not to aspiration according to the uses of each center.

## 7.4. PERMITTED AND PROHIBITED CONCOMITANT TREATMENTS

### 7.4.1. PERMITTED CONCOMITANT TREATMENTS

All drugs that, in the opinion of the principal investigator, are considered necessary for the patient's well-being and that do not interfere with the investigational product will be admitted, although they must be listed in the corresponding section of the CRD.

### 7.4.2. PROHIBITED CONCOMITANT TREATMENTS

The following medications and supportive treatments as well as procedures are prohibited during the trial:

- Any other agent under investigation
- Any surgical adhesive (Tachosil® or Hemopatch) in the control group, as well as any surgical adhesive other than Hemopatch in the experimental group.

#### 7.4.3. ADVERSE EVENT'S MANAGEMENT

Complications arising from the procedure will be treated as standard, and always at the discretion of the investigator. They should be recorded in the data collection notebook as adverse events and the treatments required as concomitant medication.

### 8. TRIAL DEVELOPMENT AND RESPONSE EVALUATION

#### 8.1. RESPONSE EVALUATION

**A- Hospital follow-up:** daily visit until hospital discharge. A daily visit will be made until hospital discharge:

##### *Clinical parameters*

- o Duration of postoperative air leakage
- o Reinsertion rate of pleural drainage for symptomatic pneumothorax.
- o 30-day postoperative readmission rate due to recurrence of symptomatic pneumothorax.
- o Cardiorespiratory related complications

##### *Radiologic parameters*

- o Presence of pneumothorax on chest x-ray

**B- Follow-up one month-3 months after hospital discharge:** FIRST POSTOPERATIVE VISIT IN CONSULTATION

- o To evaluate the clinical evolution, especially in relation to the appearance of complications. Data collection: special attention to the patient's clinical situation.
- o Radiological: Chest Rx, PA and L projections.

#### 8.2. CLINICAL TRIAL DEVELOPMENT

The Hemopatch product administration procedure (day 0 of the study) and the rest of the study visits and procedures will take place in each of the participating hospitals.

**-Visit 1: Selection:** The selection of candidate patients will be made by the Thoracic Surgery Department of each participating hospital. During this visit, and once the usual evaluation has been carried out, in response to the demand for care for which he/she attends, the patient potentially suitable for the study will be informed of the objectives of the study and the overall requirements. Informed consent will be obtained prior to any study-specific assessment. The patient will then undergo a clinical evaluation to ensure compliance with the inclusion and exclusion criteria.

The patient's medical record should record how the patient agrees to participate in the HEMOPATCH/FAP/2014 clinical trial, date of consent signature, assigned patient

number and study sponsor.

The date of the visit shall be recorded and collected:

- Presentation of written informed consent.
- Medical history, including concomitant diseases and medication, supportive treatment and baseline medical conditions.
- Complete physical examination.
- Serum pregnancy test in fertile women.
- Respiratory functional evaluation
- Chest CT scan.

Once the results of all the above-mentioned procedures have been obtained, and it has been verified that all the inclusion criteria have been met and none of the exclusion criteria have been met, the patient may continue in the study and be randomized. If, on the other hand, the patient does not meet the inclusion criteria, he/she will not be able to continue in the study and the reason for the patient's non-selection must be recorded in the CRD.

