#### ***Baseline. Pre-treatment evaluation.***

*Patients who meet the inclusion criteria will be evaluated by the usual preoperative study.*

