## 6. PARTICIPANT SELECTION

### 6.1. TARGET POPULATION

The population will consist of patients undergoing scheduled anatomic lung resection (excluding pneumonectomy) and classified D, according to the postoperative prolonged air leak risk scale (index > 1.5) ( Patient age over 65 years (1 point), BMI body mass index<25 kg/m^2 (2 points), FEV1<80% (1.5 points) and presence of pleural adhesions during surgery (1 point)).

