### 6.2. INCLUSION CRITERIA

- Age between 18 and 80 years
- Patients who are going to undergo scheduled anatomical lung resection (excluding pneumonectomy).
- Patients class D on the air leak risk scale.

Patients included in the study must meet all inclusion criteria.

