### 12.1. Population for analysis

The efficacy and safety analysis will include all patients enrolled in the study. Efficacy analyses will be performed on data from the intention-to-treat population.

The term "treatment period" used for efficacy and safety analyses refers to the period from cell administration and the end-of-treatment week (+/-7 days). This period will form the basis for the efficacy and safety summaries.

The primary efficacy data set will consist of all patients in the study who have completed all treatment. Events occurring in patients who have been withdrawn early will also be included if the patients meet the withdrawal criteria.

For the primary endpoints, an analysis will be conducted using the evaluable patient data set as well as the primary efficacy data set. Summaries of the safety data will include all patients treated in the study. The primary and secondary data set will be defined in a statistical analysis plan.

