**PAL risk scale**

Class A (punctuation 0)

Class B (punctuation 1)

Class C (punctuation 1.5–3)

Class D (punctuation > 3)

Brunelli A, Varela G, Refai M, Jiménez MF, Pompili C, Sabattini A, et al. A scoring system to predict the risk of prolonged air leak after lobectomy.

Ann Thorac Surg 2010;90:204-9

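### Randomisation requires criteria that cannot be verified before surgery (adhesions seen at operation, a postoperative exclusion), and the plan does not fix when the surgeon learns the arm or who stays in the primary analysis

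*Combined protocol and SAP*

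**What the plan says.** **When randomisation is allowed.** Section 8.2, Visit 1, lists consent, history, examination, a pregnancy test, lung function and a chest CT. When those results are in, all inclusion criteria are verified and "none of the exclusion criteria have been met, the patient may continue in the study and be randomized". Product administration is the separate Visit 2. Section 5.3 likewise treats eligibility as settled at baseline: "Patients who meet the inclusion criteria will be evaluated by the usual preoperative study". Section 5.3 C randomises by order of inclusion from an Excel table handled by the data manager, and section 6.7 fixes that order at consent.

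**What must be verified.**
- Section 6.2 requires "Patients class D on the air leak risk scale". Section 6.1 counts towards that class the "presence of pleural adhesions during surgery (1 point").
- Section 6.1 gives the cut-off as "postoperative prolonged air leak risk scale (index > 1.5"), while Annex II gives "Class D (punctuation > 3").
- Section 6.3, a list of conditions that bar entry, includes "Postoperative mechanical ventilation or thoracic surgical reintervention in the month of follow-up".

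**Who is analysed.** Section 12 says results are analysed by intention-to-treat. Section 12.1 repeats this and says all enrolled patients are included. It then states: "The primary efficacy data set will consist of all patients in the study who have completed all treatment". It adds events in early withdrawals who meet the withdrawal criteria, refers to an evaluable set that it does not define, and leaves the data-set definitions to a statistical analysis plan. The trial is open-label, and the operating surgeon is always an investigator (section 5.3, Perioperative Protocol).

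**The concern.** The entry rule cannot be followed as printed. At Visit 1 nobody has seen the pleura, and nobody knows whether the patient will be ventilated or reoperated on in the following month. Sites must therefore do one of two things: decline patients whose class depends on adhesions, or randomise on an expected score and settle eligibility later.

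In the second case an eligibility item is scored, or an exclusion event occurs, after allocation and possibly with the arm known. That alone does not bias the comparison. It does so if the patient is then taken out of the analysis and such removals differ by arm. The completers definition in section 12.1 would permit removal. The intention-to-treat statements in sections 12 and 12.1 would not. At stake is whether the primary comparison remains the randomised one.

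**Working it through.** **1. The plan's own figure.** Inputs from section 5.2.2: control rate 0.27, experimental rate 0.135, two-sided alpha 0.05, 1:1 allocation, and 80% power (printed as a beta of 0.80). With p̄ = (p₁ + p₂)/2, the pooled-variance normal approximation is

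n per arm = [1.960·√(2p̄(1−p̄)) + 0.842·√(p₁(1−p₁) + p₂(1−p₂))]² / (p₁−p₂)²

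With p̄ = 0.2025 this gives 137.9, so 138 per arm and 276 in total. The planned size reproduces exactly and is not in question.

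**2. Where adhesions decide class D.** Points: age 1, BMI 2, FEV1 1.5, adhesions 1. There are 2³ = 8 pre-operative profiles.

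| Pre-operative items | Score before surgery | With adhesions | Cut-off > 3 | Cut-off > 1.5 |
|---|---|---|---|---|
| none | 0 | 1 | never | never |
| age | 1 | 2 | never | **depends** |
| FEV1 | 1.5 | 2.5 | never | **depends** |
| BMI | 2 | 3 | never | always |
| age + FEV1 | 2.5 | 3.5 | **depends** | always |
| age + BMI | 3 | 4 | **depends** | always |
| BMI + FEV1 | 3.5 | 4.5 | always | always |
| all three | 4.5 | 5.5 | always | always |

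Two of 8 profiles depend on the operative finding under each cut-off, so reconciling the cut-offs would not remove the problem. These are profiles, not shares of patients; the documents give no frequencies. The section 6.3 item is different: it is unknown at Visit 1 for all 276.

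**3. Removal for a section 6.3 event (illustration).** The counts are assumed. This is a worst case: no true effect, every removed patient leaks, and all removals come from the experimental arm. Start from 0.27 × 138 ≈ 37 leaks per arm, 37/138 = 26.8%. After removing k leaking patients, the experimental rate is (37−k)/(138−k).

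| k | Experimental rate | Rate ratio to 37/138 | Apparent reduction | p (uncorrected chi-square) |
|---|---|---|---|---|
| 3 | 34/135 = 25.2% | 0.939 | 6% | 0.76 |
| 5 | 32/133 = 24.1% | 0.897 | 10% | 0.60 |
| 10 | 27/128 = 21.1% | 0.787 | 21% | 0.28 |
| 16 | 21/122 = 17.2% | 0.642 | 36% | 0.064 |
| 17 | 20/121 = 16.5% | 0.616 | 38% | 0.046 |

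With every randomised patient kept, the ratio is 1 and the apparent reduction 0%.

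**4. Removal for absent adhesions.** Adhesions are scored before the day-5 outcome exists, and on the scale's own logic a patient without them is at lower risk. Removing k non-leaking patients from the experimental arm gives 37/(138−k): 37/135 = 27.4%, 37/133 = 27.8% and 37/128 = 28.9% for k = 3, 5 and 10. This runs against the patch, so the table in step 3 should not be applied to the adhesion route.

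**5. If eligibility used only pre-operative items.** The adhesion-dependent patients would go. At > 3 their totals are 3.5 and 4, while retained totals run from 3.5 to 5.5. At > 1.5 their totals are 2 and 2.5, while retained totals run from 2 to 5.5. The ranges overlap and profile frequencies are unknown, so the control rate could move either way. Step 1's formula with a 50% reduction gives:

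| Assumed control rate | Total needed for 80% power |
|---|---|
| 25% | 304 |
| 26% | 290 |
| 27% (plan) | 276 |
| 28% | 264 |
| 30% | 242 |

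**The case against.** **Intention-to-treat is stated.** It is, without condition in section 12 and again in 12.1, with all enrolled patients included. A reader might infer that the plan names no proper analysis population; the documents do not support that. The difficulty is contradiction: the same section gives the name of primary efficacy set to completers, leaves the evaluable set undefined and does not say what completing treatment means for a control.

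**Section 6.4 may already cover these patients.** Its withdrawal reasons include serious protocol violation, compromised health and serious adverse events, and 12.1 keeps the events of withdrawals who meet those criteria. Section 6.4 also recommends continuing once the product has been given, and section 8.2 asks for follow-up of early discontinuations where possible. These lessen the likely loss. But late-found ineligibility and the section 6.3 events are not named, so coverage rests on judgment exercised when the arm may be known.

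**Timing is not wholly open.** Sections 5.3 C and 6.7 together point to pre-operative assignment. That stands. What is missing is when the surgeon is told.

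**Class D is often settled before surgery.** That also stands: adhesions decide it for some profiles only. The postoperative exclusion has no such limit.

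**Conclusion.** The concern holds. The text requires verification at Visit 1 of two criteria that cannot be verified there, and it does not fix disclosure of the arm or the primary population. That much is certain from the wording.

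The consequences are conditional. Bias arises only if randomised patients are removed and the removals differ by arm. Under the assumed worst case for section 6.3 events, the apparent relative reduction is 6% to 21% for 3 to 10 removals.

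Three stronger readings are not supported:
- That a false positive is likely. With nothing else at work, 17 one-sided removals of leaking patients would be needed for p < 0.05; the more realistic risk is a distorted estimate.
- That any bias must favour the patch. Removal for absent adhesions could act against it.
- That restricting entry to pre-operative items would raise the control rate and leave 276 sufficient. The overlapping scores do not show this.

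The point should be fixed before the analysis. It does not invalidate the sample size as calculated.

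**What to change.** 1. **Section 6.3:** stop using postoperative ventilation and reintervention as exclusions. Keep these patients and record the events as outcomes or intercurrent events.
2. **Section 12.1:** state that the primary analysis includes every randomised patient as allocated, patched or not. Make the completers set a sensitivity analysis.
3. **Sections 5.3 C and 8.2:** either record every item used for eligibility before the arm is disclosed to the surgeon, or base eligibility on pre-operative items alone. In both cases, remove no one for adhesion findings after disclosure.

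**Cost.** A protocol amendment and possibly an allocation step in theatre. With theatre allocation, some consented patients would not be randomised; the documents do not allow the number to be estimated. With pre-operative eligibility, the 27% control rate must be rechecked: over assumed rates of 25% to 30%, the requirement runs from 304 down to 242 patients against the planned 276.

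The conflicting wordings of the class D cut-off, the BMI cut-off, the intra-operative leak check and the reinforcement rules must also be reconciled. They are separate points, and nothing here depends on how they are resolved.
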